## **5. Study population**

The patients included in this study were diagnosed and treated in the Department of General Surgery of Nanfang Hospital, Southern Medical University. Inclusion criteria are histologically confirmed non-ampulla DA includes all stages of disease at diagnosis.

### **5.1 Diagnostic criteria:**

Non-ampulla DA patients were diagnosed according to the Chinese Medical Association Clinical Diagnosis and Treatment Guidelines for Gastrointestinal Tumors (2022 edition).

## 5.2 Inclusion criteria:

- (1) At least 18 years of age;
- (2) Voluntarily sign informed consent;
- (3) Non-ampulla DA patients were diagnosed according to the Guidelines for Clinical Diagnosis and Treatment of Gastrointestinal Tumors of the Chinese Medical Association (2022 edition), including patients at all stages of diagnosis;
- (4) Unless there are no other malignant tumors in the ampulla other than DA.

## 5.3 Exclusion criteria:

- (1) Cancer of the ampulla or other forms of gastrointestinal cancer  
Medical records are incomplete
- (2) Diagnostic or therapeutic data is missing
- (3) Follow-up was lost shortly after diagnosis
- (4) The non-ampulla DA patients were judged by the investigators to be unsuitable for participating in this study

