## Summary of research scheme

Program name	Based on long-term survival outcomes of primary non-ampulla duodenal adenocarcinoma
Applicant	Nanfang Hospital of Southern Medical University
Principal investigator	[name]
Study center and director	Southern Medical University Nanfang Hospital [name]
Object of study	Duodenal adenocarcinoma (DA) patients
Objective	
Main Objective: To determine whether radical DA resection is associated with an improvement in 5-year overall survival
 
Secondary objectives: Adjuvant therapy, pancreatic invasion, and advanced tumor stage were identified as significant predictors of overall survival

Study group	Histologically confirmed non-ampulla DA (including all stages of disease at diagnosis)
Study design	Retrospective cohort study
Study duration	2024.04-2024.06
Sample size	400 cases
Inclusion criteria	
(1)At least 18 years old;
 
(2)Voluntary signing of informed consent;
 
(3)Non-ampulla DA patients were diagnosed according to the Chinese Medical Association's Clinical Diagnosis and Treatment Guidelines for Gastrointestinal Tumors (2022 edition), including patients at all stages of diagnosis;
 
(4)Unless there is no other malignant tumor diagnosed in the ampulla DA.

Exclusion criteria	
(1)Cancer of the ampulla or other forms of gastrointestinal cancer
 
(2)Incomplete medical records
 
(3)Missing diagnostic or therapeutic data
 
(4)Follow-up was lost shortly after diagnosis

Efficiency analysis	
Primary outcome measures for effectiveness analysis: median overall survival, 3 - and 5-year overall survival rates in the cohort
 
Secondary outcome measures for effectiveness analysis: Overall survival with adjuvant therapy, pancreatic invasion, and advanced tumor

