Statistic analysis	
Statistical analysis
 
Rigorous statistical methods were used to analyze the collected data. Survival outcomes, including OS and DFS, were calculated from the date of diagnosis until the date of death or last follow-up, and from the date of diagnosis until the date of disease recurrence or last follow-up of DFS. Kaplan-Meier survival curves were generated to illustrate survival trends over time, and log-rank tests were used to compare the distribution of survival among different patient subgroups. Cox proportional hazard models were used to identify independent prognostic factors affecting survival. Variables considered in the model included demographic factors (age, sex), clinical features (BMI, jaundice, bleeding, anemia), preoperative laboratory values, treatment details (radical resection, adjuvant therapy), and pathological findings (AJCC stage, tumor differentiation and lymph node involvement rate). Hazard ratios (HRs) and 95% confidence intervals (CI) were calculated to estimate the strength of the association between each variable and survival outcomes.

Follow-up visit	The patients included in this study were from a hospital cohort that included cases diagnosed and treated in the Department of General Surgery at Nanfang Hospital of Southern Medical University. Inclusion criteria were histologically confirmed non-ampulla DA, including all stages of disease at diagnosis. Patients were excluded if they had ampulla cancer or other forms of gastrointestinal cancer, had incomplete medical records, or lost follow-up shortly after diagnosis.
Statistical approach	Statistical methods SPSS 25.0 and Prism 8.0.1 software were used for all statistical analyses.
Expected progress	Expected progress: From April 2024 to May 2024, data collection, sorting and analysis will be completed. From May 2024 to June 2024, monograph writing, submission and conclusion will be completed

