## **3. Study endpoint**

3.1 Primary endpoints: Median overall survival, 3 - and 5-year overall survival rates for the cohort

3.2 Secondary endpoints: overall survival with adjuvant therapy, pancreatic invasion, and advanced tumor

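### Incomplete records and missing diagnostic or treatment data exclude patients from the whole study, although the primary OS endpoints can be estimated without most of those data

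*Combined protocol and SAP*

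**What the plan says.** Section 5.3 lists "Medical records are incomplete" and "Diagnostic or therapeutic data is missing" among the exclusion criteria. The Summary of research scheme gives the same pair, as "Incomplete medical records" and "Missing diagnostic or therapeutic data". Its follow-up row repeats the first, removing patients who "had incomplete medical records, or lost follow-up shortly after diagnosis". All of these are conditions of entry to the study. No section says which items must be present or how much may be missing, and none limits the rule to a particular model.

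Section 3.1 gives the primary endpoints: "Median overall survival, 3 - and 5-year overall survival rates for the cohort". The statistical analysis row of the Summary says survival outcomes "were calculated from the date of diagnosis until the date of death or last follow-up". The same row lists the Cox covariates, which include preoperative laboratory values and "pathological findings (AJCC stage, tumor differentiation and lymph node involvement rate". Section 10 has no missing-data method, no sensitivity analysis, and no plan to count or describe the patients excluded. Section 8 ends collection once 400 patients are enrolled.

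**The concern.** The completeness rule acts at entry, so it governs every analysis, including those that do not use the missing item. Handling incomplete covariates is a real question for the Cox model. For a Kaplan-Meier curve of the whole cohort it does not arise, because no covariate enters the estimate. Removing a patient with known dates and vital status gains nothing for the primary endpoints, and it makes the cohort depend on how well each patient was documented.

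This matters if documentation is related to prognosis. The study is meant to cover all stages at diagnosis, and its main objective concerns radical resection. Patients who were not resected, or who died soon after diagnosis, may plausibly have thinner records. If so, cohort OS would be too high and the non-resected comparison group would be distorted. Because collection stops at 400 and exclusions are not counted, a reader could not see how many patients had been passed over.

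**Working it through.** **What each analysis needs**

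| Analysis | Data required | Source |
|---|---|---|
| Cohort median, 3- and 5-year OS | Confirmed non-ampullary DA, diagnosis date, date of death or last follow-up, vital status | Section 3.1; Summary, statistical analysis row |
| Resection and 5-year OS | The above plus radical-resection status | Section 2.1 |
| Cox model | The above plus demographic, clinical, laboratory, treatment and pathology covariates | Summary, statistical analysis row |

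Only the last row needs the full work-up, yet the exclusion applies to all three.

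**Plan's own figure.** The sample size of 400 cannot be reproduced. Section 10.1 gives no effect size, power, event count or precision target. The number of patients excluded and their survival are not given either, so everything below rests on assumed inputs.

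**Effect on the cohort OS rate.** Let f be the share of otherwise eligible patients excluded, and let S_in and S_out be 5-year OS in retained and excluded patients.

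- All-patient rate = (1 - f) x S_in + f x S_out
- Overstatement = f x (S_in - S_out)

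Assume S_in = 40% and S_out = 10% to 20%, a gap of 20 to 30 points:

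| f | Eligible patients behind 400 retained, 400/(1 - f), rounded up | All-patient 5-year OS | Overstatement |
|---|---|---|---|
| 5% | 422 | 38.5-39% | 0.05 x 20 to 30 = 1-1.5 points |
| 10% | 445 | 37-38% | 0.10 x 20 to 30 = 2-3 points |
| 20% | 500 | 34-36% | 0.20 x 20 to 30 = 4-6 points |

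If S_out equals S_in the bias is zero. If excluded patients survive longer, the sign reverses: a gap of -10 points at f = 20% gives -2 points.

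**Comparison with sampling error.** With 400 patients, no censoring and a true rate of 40%, the 95% confidence half-width is 1.96 x sqrt(0.40 x 0.60 / 400) = 4.8 points. The assumed bias is below this at 5-10% excluded and comparable to it at 20%.

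**How far f is left open.** If k items are each missing independently with probability m, a rule that allowed no gaps would remove 1 - (1 - m)^k. With m = 2%, this is 1 - 0.98^10 = 18% for 10 items and 1 - 0.98^14 = 25% for 14. A lenient reading of the same words could remove almost nobody. The text does not say which is meant.

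**The case against.** A reader might infer that one missing laboratory or pathology item removes a patient. The documents do not say so. Neither criterion contains the word any or a threshold, and a natural reading is that the diagnosis or the treatment itself is undocumented. Section 6.4 collects genetic markers only where available, so some gaps appear to be tolerated. This objection stands. What remains is that the rule is undefined and applies to the whole study.

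A reader might also infer that unresected patients are excluded because they have no lymph node result. That would conflict with the all-stages population and would empty much of the comparison group. A result that cannot exist without surgery is better called not applicable than missing. Nor do the documents say that unresected patients lack CEA or CA19-9. Preferential loss of unresected or early-dying patients is therefore plausible but not established.

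A third inference is that OS is overstated as a matter of fact. The documents cannot show this, because direction and size depend on quantities they do not give. For the main objective the effect could even be conservative: losing the worst-prognosis unresected patients would flatter that group and shrink the apparent association with resection.

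Finally, some diagnostic and treatment data are legitimately required. Histology must be confirmed, ampullary cancer ruled out, and resection status known for the resection comparison. That limits the remedy, but it does not justify a completeness rule for the cohort OS estimates.

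**Conclusion.** The point holds in a limited form. As written, the two criteria remove patients whose OS could be estimated, and nothing in Section 10 confines the rule to the Cox model or deals with missing data. This loses usable information on the primary endpoints and opens a route for selection.

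Upward bias in cohort OS is conditional on excluded patients having worse survival. The illustrated range, 1 to 6 points on 5-year OS, rests entirely on an assumed 40% in retained patients, 10-20% in excluded patients, and 5-20% excluded. The effect on the resection comparison is distortion of unknown direction. The plan should be changed because the better method is specific and cheap, and does not depend on how large the bias turns out to be.

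**What to change.** - Replace the two exclusions, in Section 5.3 and in the Summary, with a minimum data set for entry: histologically confirmed non-ampullary DA, a diagnosis date, and vital status or date of last follow-up.
- Include every otherwise eligible patient who meets it in the Kaplan-Meier OS analyses.
- Require known radical-resection status only for the resection comparison.
- Code items that exist only after surgery, such as the lymph node involvement rate, as not applicable, and use them only in a model restricted to resected patients.
- Handle other missing baseline covariates within the Cox model, for example by multiple imputation, with the complete-case fit as a sensitivity analysis.
- Report the number, characteristics and OS of patients with incomplete data.

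This is a cheap improvement: new plan wording, somewhat more record abstraction and analysis, and possibly a slightly less favourable OS. It does not address the exclusion of patients lost soon after diagnosis or the signed-consent requirement, which are separate routes of selection.

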## **2. Study purpose**

2.1 Main Objectives: Whether radical DA resection is associated with improvement in 5-year overall survival

2.2 Secondary objectives: Adjuvant therapy, pancreatic invasion, and advanced tumor stage were identified as significant predictors of overall survival

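### Patients lost *shortly* after diagnosis are excluded with no time limit, although overall survival starts at diagnosis and they could be censored; the cohort cannot be reproduced, and the effect on survival is uncertain in sign and probably modest

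*Combined protocol and SAP*

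**What the plan says.** Section 5.3, item (3), excludes a patient when "Follow-up was lost shortly after diagnosis". The synopsis has the same item among its exclusion criteria, and its follow-up row again excludes those who "lost follow-up shortly after diagnosis". None of the three places says how many days or months count.

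The synopsis row on statistical analysis has OS "calculated from the date of diagnosis until the date of death or last follow-up", analysed by Kaplan-Meier, log-rank and Cox. Section 3 sets the primary endpoints: "Median overall survival, 3 - and 5-year overall survival rates for the cohort". The main objective in section 2.1 is "Whether radical DA resection is associated with improvement in 5-year overall survival".

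Other rules act on the same patients:
- Section 5 limits the population to cases both diagnosed and treated in one surgical department.
- Section 5.2 requires patients to "Voluntarily sign informed consent", and section 6 requires this before data are collected.
- Section 5.3 also excludes where "Medical records are incomplete" or "Diagnostic or therapeutic data is missing".
- Section 5.4 lists loss to follow-up as a reason for withdrawal.
- Section 8 ends collection at 400 patients.

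**The concern.** A patient with a diagnosis date and a later last contact has a valid censored OS time. Excluding that patient makes membership of the cohort depend on something that happens after time zero. Diagnoses span 2009 to 2023 (section 4) and data are collected in April and May 2024 (section 11.4.3), so whoever decides what *shortly* means can usually already see the outcome. Two abstractors could build different cohorts from the same charts.

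At stake are the primary OS figures, which describe whatever cohort this rule leaves. The resection comparison is also at stake if early loss is more common in unresected patients. The plan does not ask for the number excluded, so a reader could not judge the effect afterwards.

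**Working it through.** **Inputs.** The plan has no figure to reproduce: it gives no loss rate, no expected survival and no derivation of the 400. From the documents come only n = 400, the OS definition and the 2009-2023 span. Assumed: exponential survival with median 24 or 36 months (rate λ = ln 2/median), early window *w* of 3 or 6 months, and the loss shares below.

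**1. Yardstick.** The 95% half-width of a survival rate at n = 400 is 1.96 × √(S(1−S)/400): 4.9 points at S = 0.50 and 4.5 at S = 0.30.

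**2. Loss unrelated to prognosis, early deaths retained.** A share *p* would lose contact at a time uniform on 0 to *w*. Those who die first are observed deaths and stay in; their share is P = 1 − (1 − e^(−λw))/(λw). Censoring recovers S(36). Exclusion gives (1−p)S(36) / [(1−p) + pP].
- p = 0.10, w = 3, median 36: P = 0.0283; 0.45/0.9028 = 0.4984 against 0.5000, or −0.16 points.
- p = 0.30, w = 6, median 24: P = 0.0818; 0.2475/0.7245 = 0.3416 against 0.3536, or −1.2 points.

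Simulation with 600,000 patients per scenario and end-of-study censoring gave 0.16 to 1.19 points at 3 years and 0.08 to 0.73 at 5 years. Stretching the window to 12 months with 30% lost takes the 3-year figure to about 2.2.

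**3. Lost patients have a worse prognosis.** With share *f* lost soon after diagnosis, exclusion overstates by f × [S_kept(36) − S_lost(36)].
- Twice the hazard, 5-year OS 40% in the others: S_kept(36) = 0.40^0.6 = 0.577; S_lost(36) = 0.577² = 0.333; difference 0.244. This gives 1.2 points at f = 5% and 2.4 at f = 10%. With loss spread over 6 months, simulation gives 0.95 and 1.88.
- Every lost patient dies at 3-12 months: S_lost(36) = 0. At f = 10% and median 36, true OS is 0.90 × 0.50 = 45.0% and the excluded figure is 50.0%, an overstatement of 5.0 points. At median 24 it is 0.10 × 0.3536 = 3.5 points. At f = 20% these double.

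In the 10%, median-36 case, censoring gives 50.1% to 50.2% by simulation, no better than exclusion. Counting the lost as dead gives 45.0%; assuming them alive gives 45.0 + 10.0 = 55.0%.

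**4. Other rules also remove a share *q* of deaths inside the window.** Exclusion then gives (1−p)S(36) / {(1−p)S(w) + (1−q)[(1−p)(1−S(w)) + pP]}. Take w = 6, median 24, q = 0.25, with S(6) = 0.8409 and true S(36) = 0.3536.
- No early loss (p = 0): 0.3536/(0.8409 + 0.75 × 0.1591) = 0.3682, an error of +1.5 points due to the other rules alone.
- 30% lost and excluded: 0.2475/[0.5886 + 0.75 × (0.1114 + 0.0245)] = 0.3584, or +0.5.
- 30% lost and censored: about +1.5, by numerical integration of the Kaplan-Meier hazard.

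Here the overstatement belongs to the other rules. The early-loss exclusion partly offsets it, and censoring uncovers it again. With p = 0.10 and q = 0.50 the errors are about +2.8 excluded and +3.0 censored.

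**5. Resection comparison (simulation, true HR 1, 6-month window).** With non-informative loss in 3% of resected and 20-30% of unresected patients, the HR is 0.94-0.99 after exclusion and 0.99-1.01 with censoring. If instead 30-50% of unresected deaths before 6 months are recorded as losses, it is 1.04-1.18 excluded and 1.04-1.19 censored.

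**The case against.** The case for leaving the rule alone is substantial.

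- **Overlap.** A patient lost before treatment is arguably outside the section 5 population already, and would often fail the consent, incomplete-record or missing-data rules. Deleting item (3) may restore few patients. This stands.
- **Later losses are covered.** A reader might infer from section 5.4 that the plan has no rule for enrolled patients lost later. It does: OS ends at death or last follow-up, which is ordinary censoring. Section 5.4 needs only a cross-reference.
- **Censoring does not rescue the harder cases.** Steps 3 and 4 confirm this. It removes the selection artefact of step 2 and nothing else.
- **The 400 limit.** If it binds, restored patients with very short follow-up may displace patients followed for longer. This stands as a cost.
- **Defining the window would be enough.** This does not fully stand. A defined window makes the rule repeatable, but patients are still chosen on a post-diagnosis event, and nothing shows how far the results depend on them. Patients with no usable record are already covered by the other exclusions, so what item (3) adds is mainly the removal of usable short follow-up.

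**Conclusion.** The point holds in a limited form. An undefined exclusion, applied after outcomes are known, selects the cohort for the primary endpoints, so that cohort is not reproducible and may be selected.

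A reader might go further and infer that the rule inflates survival. The documents do not support that. The sign depends on why patients were lost and on what the other rules remove: 3-year OS is too low by 0.16 to 1.2 points in step 2, and too high by about 1 to 5 points with 5-10% lost in step 3. Nor does the rule itself remove early deaths; where those go missing, the cause is the consent, missing-data or department-treatment rules. It would equally be wrong to infer that censoring cures the problem.

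Up to about 10% lost, these effects are no larger than, or about equal to, the 4.5-4.9 point half-width. That they are modest cannot be confirmed, because no loss rate is stated; 20% lost with very poor prognosis would exceed it. Priority: minor to moderate.

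**What to change.** - Delete the early-loss exclusion in section 5.3, item (3), and in both synopsis rows. Keep every otherwise eligible patient from diagnosis, censored at the date last known alive.
- State in section 5.4 that the synopsis rule ending OS at last follow-up applies to patients lost to follow-up.
- Report the number lost within a pre-stated window (for example 6 months) by resection status. Report also how many patients, and how many early deaths, the consent, missing-data, incomplete-record and department-treatment rules remove.
- Add two bounding sensitivity analyses for the early losses: counted as deaths at last contact, and assumed alive to the data cut-off.
- State that censoring corrects neither informative loss nor the removal of early deaths by other rules.

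**Cost.** Protocol wording, one table and two extra runs. Some patients will contribute very short follow-up, may displace longer-followed patients if the 400 limit binds, and may be few. The bounds widen as early loss grows: at 10% lost they span 45.0% to 55.0% in the step 3 example.

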## **4. Study design**

This retrospective analysis was designed to clarify long-term survival outcomes in patients diagnosed with non-ampulla DA. The study spans a 15-year period, from 2009 to 2023, capturing a comprehensive dataset that reflects advancements in diagnostic and treatment strategies over time. This cohort of 400 patients was carefully selected to provide a robust data set for analyzing survival outcomes and identifying prognostic factors affecting overall survival (OS) and disease-free survival (DFS).

No randomized or any protocol-driven treatment will be administered or provided to the subjects during the study. If clinically applicable, treatment decisions and treatment options are made at the discretion of the treating physician.

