## 5.4 Case withdrawal and exfoliation

- (1) All enrolled subjects have the right to withdraw from the study at any time. Reasons for case withdrawal:
  - (2) The subjects asked to withdraw and did not want to continue to participate in the study;
  - (3) Subjects lost follow-up;
  - (4) Participants were deemed unfit to continue in the study for other reasons;
  - (5) The subjects were also participating in other studies.

Subjects who dropped out of the study were considered as shedding cases. When the patient falls off, the patient should be contacted as far as possible, evaluate the project and fill out the research summary page.

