#### 11.4.3 Expected progress and completion date of the clinical study

From April 2024 to May 2024, data collection, sorting and analysis will be completed.

From May 2024 to June 2024, I completed the writing, submission and conclusion of the monograph.

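### Sections 5.3(4) and 5.4(4) allow exclusion or removal on unstated investigator judgement in a chart review where outcomes can be visible, and the synopsis has no such exclusion

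*Combined protocol and SAP*

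**What the plan says.** Section 5.3 (Exclusion criteria) ends with item (4): "The non-ampulla DA patients were judged by the investigators to be unsuitable for participating in this study". It does not say on what grounds, by whom, at what point, or with what record. Section 5.4 (Case withdrawal) lists as one reason for removal: "Participants were deemed unfit to continue in the study for other reasons". The other reasons are not stated either.

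The synopsis differs. Its exclusion list has four items, the last being "Follow-up was lost shortly after diagnosis". Its Follow-up visit row restates most of that list, excluding patients who had ampullary or other gastrointestinal cancer, or who "had incomplete medical records, or lost follow-up shortly after diagnosis". Neither place mentions investigator judgement.

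The design is a "Retrospective cohort study". Section 4 states: "The study spans a 15-year period, from 2009 to 2023". Section 11.4.3 gives the timetable: "From April 2024 to May 2024, data collection, sorting and analysis will be completed". Section 6.3 takes the data from routine clinical records, and Section 6.4(3) collects survival time and recurrence together with presentation and treatment. The primary endpoints in Section 3.1 are "Median overall survival, 3 - and 5-year overall survival rates for the cohort", and the main objective in Section 2.1 is the association of radical resection with 5-year overall survival.

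**The concern.** In a prospective trial, a clause of this kind is normally applied before treatment, when nobody knows the outcome, and it protects patients. Neither feature is present here. Section 4 says that no protocol-driven treatment is given and Section 6 says that no extra visits or tests are needed, so the clause has no treatment-safety purpose. The person judging suitability may be reading a chart that already records a recurrence or a death.

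The usual legitimate reasons for dropping a case are covered elsewhere: inadequate records, missing data and early loss to follow-up in Section 5.3, refusal in Section 5.2(2), and withdrawal on request in Section 5.4(2). What remains for 5.3(4) is judgement on unspecified grounds. If that judgement is related to survival, even unintentionally, it biases the cohort survival estimates. If it is also applied unevenly between resected and non-resected patients, it biases the comparison that is the main objective.

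**Working it through.** The plan gives no figure for this point. Its only planning number is 400, with no derivation. The check is therefore mainly a comparison of the text, followed by an illustration.

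**1. The exclusion lists side by side**

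| Ground | Synopsis, exclusion list | Synopsis, Follow-up visit row | Section 5.3 |
|---|---|---|---|
| Ampullary or other GI cancer | yes | yes | yes |
| Incomplete records | yes | yes | yes |
| Missing diagnostic or treatment data | yes | no | yes |
| Early loss to follow-up | yes | yes | yes |
| Investigator judges unsuitable | **no** | **no** | **yes** |

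The lists give different cohorts whenever 5.3(4) is used.

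**2. Can the outcome be visible when eligibility is judged?** Cases run from 2009 to 2023 and data collection is April to May 2024, so any death or recurrence already in the chart can be seen, whatever the year of diagnosis. Complete 5-year status is available only for diagnoses up to about May 2019. From January 2009 that is about 10.4 of 15 calendar years (10.4/15 = 69%). The plan does not state whether eligibility is settled before or after outcomes are abstracted.

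**3. Is there a safeguard elsewhere?** I found no requirement for consecutive cases, for eligibility review without sight of outcome, or for a screening log or flow table. Sections 4 and 10.1 describe the cohort as selected with care. Section 8 ends collection at 400 enrolled, so a case set aside before enrolment can be replaced without any trace in the final number.

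**4. Illustration.** All inputs except 400 are assumed, and crude proportions stand in for Kaplan-Meier estimates.

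Assume true 5-year survival of 40%, or 160 of 400. Removing k patients who died before 5 years gives 160/(400 − k):

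- k = 8: 160/392 = 40.8% (+0.8 points)
- k = 12: 160/388 = 41.2% (+1.2)
- k = 20: 160/380 = 42.1% (+2.1)

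Refilling to 400 with average patients changes little: for k = 20, (160 + 0.4 × 20)/400 = 42.0%. Removing 20 five-year survivors instead gives 140/380 = 36.8% (−3.2).

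For the resection contrast, assume 120 non-resected patients with 24 alive at 5 years (20.0%). That leaves 136 of 280 resected (48.6%) and a difference of 28.6 points.

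- 20 early deaths removed from the non-resected group: 24/100 = 24.0%, difference 24.6
- 20 early deaths removed from the resected group: 136/260 = 52.3%, difference 32.3

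So the same number of removals can shrink or widen the contrast, depending on where they fall.

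**The case against.** Five objections deserve an answer.

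*Consent.* Sections 5.2(2), 6 and 6.1 require signed consent before data collection and as a condition of enrolment, and the available text shows no waiver or proxy route. Read literally, patients who have died cannot enter, and 5.3(4) would have no early deaths to remove. This stands as a limit on the illustration. It does not remove the problem, because recurrence and follow-up to date are still visible for living patients and the clause is still open-ended. The consent rule is a separate selection question that the sponsor should reconcile in its own right.

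*Survival already known.* A reader might infer that every exclusion is made with survival known. The documents do not support that. Visibility follows from the design and dates, the order of screening and abstraction is not stated, and 5-year status is incomplete for diagnoses after about mid-2019. What is supported is that the outcome can be visible.

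*Irreparable bias.* A reader might also infer that such exclusions could never be audited or corrected. That goes too far. The charts remain and could be re-screened, Sections 9.1, 11.1(4) and 11.4.2 provide for source records, verification and quality checks, and Section 5.4 asks for a summary page for patients who drop out. The real gap is that no log is required for patients excluded before enrolment.

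*Size.* On the assumed values, the shift of 0.8 to 2.1 points is smaller than the sampling half-width of 1.96 × √(0.4 × 0.6/400) = 4.8 points. That is true, but sampling error is reported in a confidence interval and selection bias is not.

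*Section 5.4(4).* With no visits or study treatment, this clause may rarely be used. That is fair. It is the weaker of the two clauses, though for the same reason it serves little purpose.

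**Conclusion.** The point holds as a permitted route to bias. Section 5.3(4), and to a lesser extent 5.4(4), allow patients to be left out on unstated judgement when their outcome can be seen. The synopsis does not contain the exclusion, and nothing in the plan controls or records its use. Overall survival and the resection contrast could be biased in either direction.

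The documents do not show that any patient was excluded because of outcome, and they give no basis for estimating how many might be. The shifts of 0.8 to 2.1 points in cohort survival, and of about 4 points either way in the contrast (28.6 to 24.6 or 32.3), rest on assumed survival, group sizes and numbers removed. They also require that patients who died can enter despite the consent rule. The case for change rests on the wording and the missing safeguards, not on those figures.

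**What to change.** 1. Delete 5.3(4) and 5.4(4).
2. Make the exclusion lists in Section 5.3 and the synopsis identical, including the Follow-up visit row, with objective criteria only.
3. State that eligibility is decided without reference to vital status or recurrence. Screening cannot use the diagnosis record alone, because missing treatment data and early loss to follow-up are both judged from later records. Allow those records to be consulted only as far as needed to check record completeness, treatment data and early loss to follow-up.
4. Log every exclusion with its reason and report the counts in a flow table.

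If the sponsor wishes to keep a judgement clause, the minimum is to define its grounds in advance, apply it blind to outcome, log each use, and run a sensitivity analysis that adds those patients back.

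The cost is small but not nil: a protocol amendment with ethics approval (Sections 11.3 and 12.1) and a little more screening work. No new data source is needed.
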